2.4.1 Rationale for dose and schedule selection

The recommended dose for brentuximab vedotin per its prescribing information is 1.8 mg/kg via intravenous (IV) infusion administered every 3 weeks. This dose and schedule was evaluated in two pivotal Phase 2 studies (SG035-0003 and SG035-0004) in patients with CD30-positive hematologic malignancies.

The dose for nivolumab for this study is 3 mg/kg via IV infusion administered every 3 weeks. The approved dose for nivolumab as monotherapy is 3 mg/kg every 2 weeks for the treatment of melanoma and metastatic squamous non-small cell lung cancer. However, nivolumab has been studied as monotherapy and in combination treatment in several tumor types with every 3 week dosing. It was recently reported that nivolumab dose levels of 0.3, 2, and 10 mg/kg every 3 weeks yielded similar ORR, PFS, and OS in a Phase 2 trial of patients with metastatic renal cell carcinoma [33]. Moreover, nivolumab dose levels of 0.1, 0.3, 1, 3, and 10 mg/kg every 2 weeks were associated with very similar (median 64%–70%) PD-1 receptor occupancy and comparable ORR and PFS in patients with advanced melanoma [34]. These findings indicate a flat dose-response relationship for nivolumab across a wide dose range for both every 2- and 3-week dosing, suggesting that dosing nivolumab at 3 mg/kg every 3 weeks is appropriate in the current study.

By delivering brentuximab vedotin, a directly cytotoxic agent, together with nivolumab in Cycle 1 it is anticipated that tumor-associated antigens will be released and available for presentation to resident cytotoxic T-cells at the same time that these cells become activated through PD-1 blockade.

Participants will be treated at the doses and schedule deemed safe in the currently ongoing Phase 1/2 study of nivolumab plus brentuximab vedotin as initial treatment of participants with relapsed/ refractory HL after failure of front-line therapy (NCT02572167), except that the drugs will both be given on day 1 of

cycle 1. This change is supported by the safety demonstrated in an ongoing clinical trial (NCT01896999) evaluating the same combination in patients with relapsed or refractory HL in second-line or beyond. In that trial, the rate of infusion reactions was < 10% in that trial, as compared to the 38% infusion-related reaction rate observed in NCT02572167 (both studies presented at ASH 2016). NCT02572167 is being amended to enroll additional patients dosing both medications on Day 1 of Cycle 1.

For this study, we will decrease the number of cycles of post-ASCT consolidation to 8 cycles as compared to 16 cycles in the AETHERA trial [32]. If BV is moved to first line therapy based on the ECHELON-1 trial (NCT01712490), patients will be receiving the equivalent of 6 cycles as a part of induction. Additionally, BV (alone or in combination) as first salvage therapy is being investigated, and patients who receive the agent prior to ASCT typically receive 4 cycles. Most importantly, in the AETHERA trial, the median number of cycles BV completed for patients who completed fewer than 16 cycles was 10.5 cycles [32]. Therefore, since 16 cycles is the maximum number of cycles to be administered in a single patient, many patients will have received 4-6 cycles of BV as part of prior therapy and 10 cycles appeared to be the inflection point for discontinuation of BV for toxicity on the AETHERA trial [32], we chose 8 cycles to stay short of the toxicity inflection point and keep patients from receiving more than 16 total cycles. In addition, other ongoing studies of single-agent PD-1 inhibition as post-ASCT consolidation in HL are employing 8 cycles, therefore, the 8 cycles utilized here will be consistent with the prior experience of anti-PD1 post-ASCT consolidation.

2.4.2 Rationale for correlative studies

The correlative analyses that will be performed as part of this clinical trial are exploratory and intended to generate hypotheses that can be validated in a larger study. The rationale for specific proposed correlative studies is included below, though the list of possible correlative studies is not necessarily exhaust, as it is anticipated that the exact nature and type of correlative studies may change as new scientific data emerges during the course of the study.

2.4.2.1 Minimal Residual Disease Assessment

Circulating tumor DNA detection has been examined in lymphoma. Next-generation sequencing (NGS)-based ctDNA detection performed by NGS of the immunoglobulin (Ig) or T-cell receptor genes (Ig-NGS) can identify ctDNA in the peripheral blood mononuclear cells (PBMC) and plasma (cell-free ctDNA) at diagnosis in patients with a range of lymphomas, including classical Hodgkin lymphoma and DLBCL.[35-38] In addition, ctDNA levels (measured by Ig-NGS) track with treatment response in DLBCL, and the persistence or recurrence of ctDNA during and after upfront therapy is associated with subsequent DLBCL relapse.[37, 38] Following allogeneic hematopoietic stem cell transplantation in patients with lymphoma or chronic lymphocytic leukemia (CLL), the presence of ctDNA (Ig-NGS) is associated with a higher risk of subsequent relapse and poorer progression-free survival (PFS).[39-41] Moreover, we have demonstrated that ctDNA assessment is a biomarker of outcome in patients with DLBCL who undergo autologous hematopoietic stem cell transplantation.[42]

2.4.2.2 9p24.1 Abnormalities in HL

Frequent genetic alterations in the 9p24.1 region, which includes the *PD-L1* and *PD-L2* loci, have been observed in HL [8]. *PD-L1* gene amplification has been linked with increased expression of PD-L1 in HL tumor samples [8]. In addition, the *JAK2* locus is contained within the 9p24.1 region, and *JAK2* activation upregulates *PD-L1* transcription and expression [8]. Furthermore, Epstein-Barr virus infection, which is frequently observed in HL, has also been identified as a mechanism of *PD-L1* upregulation and expression

in HL.[23] These findings support the concept that the PD-1/PD-L1 pathway plays a key role in host immune evasion that is central to HL pathogenesis,[8] and provides a strong rationale for the use of PD-1/PD-L1 pathway inhibitors in HL.

Although genetic alterations in the 9p24.1 region are nearly universal in HL patients, inferior outcomes after standard initial treatment are observed in patients with amplification (3 or more copies, 36% of patients at diagnosis) of 9p24.1.[43] While genetic alterations in the 9p24.1 region are commonly observed in patients with HL treated with PD-1 inhibitors [24], the specific types of 9p24.1 alterations have not been examined for association with outcome after PD-1 inhibition.

2.4.2.3 Gene Expression Profiles

In HL patients treated with standard induction chemotherapy, gene expression profiles (GEP) of HL tissue samples, which includes GEP of both the tumor microenvironment (TME) and tumor cells, are associated with outcomes[44-46]. Studies have shown that GEP of genes associated with macrophage activation, the cell cycle, and apoptosis can identify high-risk subsets of patients with poorer survival.[44-46]

Gene expression profiles are associated with outcome after immune checkpoint inhibitor therapy in patients with advanced melanoma. Increased expression of genes that encode for immune-related targets, such as T-cell surface markers, immune receptors, and cytokines/chemokines, in pre-treatment melanoma tumor samples are associated with response to the CTLA4 inhibitor, ipilimumab.[47] In addition, a set of gene expression signatures (upregulation of genes associated with mesenchymal and inflammatory tumor phenotypes, angiogenesis, and wound healing) were enriched in melanoma patients who failed to respond to PD-1 inhibitors (nivolumab and pembrolizumab).[48]

Given the key role of the TME in response to anti-PD-1 therapy as well as in the pathogenesis of HL, we hypothesize that GEP will highlight features of the HL TME in pre-treatment tumor tissue that will be associated with outcome in patients with relapsed or refractory HL treated with PD-1/PD-L1 pathway inhibitors.

2.4.2.4 Multiplexed Immunohistochemistry

The composition and spatial orientation of immune cells and immune checkpoints in and around a tumor is associated with outcome after checkpoint inhibitor therapy. Specifically, the pre-treatment density of CD8+ T-cells, PD-1+ cells, and PD-L1+ cells in melanoma tumors and at the invasive margin is associated with response to pembrolizumab therapy. In addition, the proximity between CD8+ T-cells and PD-L1+ cells in and around melanoma tumors is associated with response to therapy.[49] On treatment biopsies revealed that patients responding to anti-PD-1 therapy had an increase in intratumoral CD8+ T-cells when compared to non-responders. These findings suggest that the melanoma patients who are most likely to respond to PD-1/PD-L1 pathway inhibitors had adaptive immune resistance, an underlying immune response that was shut down by the PD-1/PD-L1 pathway and released by anti-PD-1 therapy.

HL is histologically defined by few Hodgkin Reed-Sternberg (RS) cells surrounded by an ineffective, mixed immune infiltrate. The nearly universal genetic alterations in the *PD-L1* and *PD-L2* loci observed in RS cells, which results in increased expression of PD-L1 on RS cells, suggests that exploitation of the PD-1/PD-L1 pathway to evade the host immune response is fundamental to the pathogenesis of HL.[8] In addition, multispectral imaging-based multiplexed immunohistochemistry has demonstrated that the majority of PD-L1 expressing cells in the HL TME are tumor-associated macrophages, which appear to have PD-L1 expression induced by RS cells (Carey et al., ASH 2015). Despite this underlying dependence on the PD-1/PD-L1 pathway, not all patients respond to PD-1/PD-L1 pathway inhibitors, and some responding

patients have a short duration of response. We hypothesize that there are differences in the TME, specifically the phenotype and spatial orientation of the immune cells in the TME and their proximity to PD-L1 expressing cells and RS cells, which predict response to nivolumab and/or NICE therapy.

2.4.2.5 Impact of Study Treatment on Immune Reconstitution after ASCT

Anti-PD-1 therapy increases the number of cytotoxic T lymphocytes in the peripheral blood, and results in increased IFN-gamma levels and upregulation of IFN-gamma gene target expression. [26, 50] Checkpoint inhibitor therapy, including anti-CTLA4 and anti-PD-1 therapy, also impacts peripheral blood T-cell receptor repertoire (TCR) diversity.[51, 52] Immune reconstitution after autologous stem cell transplantation (ASCT) is well studied, but no there are no data describing immune reconstitution in the setting of ongoing anti-PD-1 therapy. We hypothesize that patients treated with brentuximab vedotin and nivolumab will have earlier and enhanced reconstitution of effector T-cell subsets, and earlier recovery of and broader TCR diversity.

3.0 ELIGIBILITY CRITERIA

Participant MRN (COH Only):	Participant Initials (F, M, L):
Institution:	

Participants must meet the following criteria on screening examination to be eligible to participate in the study:

3.1 Inclusion Criteria

Informed Consent and Willingness to Participate

- 1. Documented informed consent
- 2. Agreement to allow the use of archival tissue from pre-ASCT tumor biopsies (See [Section 9.2](#) for details)
 - If unavailable, exceptions may be granted with Study PI approval.

Age Criteria and Performance Status

- 3. Age: \geq 18 years
- 4. ECOG performance status \leq 2 (See [Appendix A](#))

Nature of Illness and Treatment History

- 5. Histologically confirmed diagnosis of classical Hodgkin lymphoma (excluding nodular lymphocyte predominant Hodgkin lymphoma) according to the WHO classification, with hematopathology review at the participating institution.
- 6. Have high-risk relapsed or refractory Hodgkin lymphoma (HL), defined as at least one of the following:
 - Primary refractory disease to front-line therapy.
 - Relapse within 1 year of completing front-line therapy.
 - Extranodal involvement at the time of pre-ASCT relapse.
 - B symptoms at pre-ASCT relapse.
 - More than one type of pre-ASCT salvage therapy required.
- 7. Planning to receive or have received autologous stem cell transplantation (ACST) per institutional standards as part of standard of care.
 - **Pre-ASCT participants** may consent but will not be eligible to begin treatment until after ASCT, and will have to fulfill all inclusion and exclusion criteria before starting protocol therapy.
 - **All participants** must initiate Day 1 of protocol therapy **within 30-60 days post stem cell reinfusion**. Study PI can grant exception for a patient to start as late as 75 days post stem cell reinfusion with a reasonable justification for delay (e.g. recovery from post-ASCT toxicity) and this will not be a protocol deviation, nor require an exception to be filed.
- 8. Recovery from ASCT toxicity as defined as outpatient status, able to drink, eat normally, and do not need intravenous hydration prior to Day 1 of therapy
- 9. Achieved at least stable disease to salvage treatment determined by PET/CT using 2014 Lugano Classification [2] prior to ASCT.
- 10. Brentuximab vedotin naïve OR had at least stable disease by Lugano Classification to prior brentuximab vedotin treatment

Participant MRN (COH Only):

Participant Initials (F, M, L):

Institution:

Organ Function Criteria and Pregnancy11. ANC \geq 1000/mm³12. Platelets \geq 50,000/mm³13. Hemoglobin \geq 8 g/dL14. Total bilirubin \leq 1.5 x ULN OR 3 x ULN for Gilbert's disease15. AST and ALT \leq 2.5 x ULN16. Creatinine clearance* \geq 40 mL/min per 24 hour urine collection or the Cockcroft-Gault formula

* Calculated per institutional standard

$$\text{CrCl} \text{ (mL/min)} = \frac{(140\text{-age}) \times \text{actual body weight (kg)}}{72 \times \text{serum creatinine (mg/dL)}} \text{ (x 0.85 for females)}$$

Or

$$\text{CrCl} \text{ (mL/min)} = \frac{(140\text{-age}) \times \text{actual body weight (kg)}}{0.8136 \times \text{serum creatinine (umol/L)}} \text{ (x 0.85 for females)}$$

17. Forced expiratory volume in one second (FEV1) and carbon monoxide diffusion capacity (DLCO) (adjusted for Hb) \geq 50% adjusted18. WOCBP only: Negative urine or serum pregnancy test (minimum sensitivity 25 IU/L or equivalent units of HCG)

- If the urine test is positive or cannot be confirmed as negative, a serum pregnancy test will be required

ANC:	Date:
Plts:	Date:
Hgb:	Date:
ULN:	Date:
Bil:	
ULN: ALT:	Date:
ULN: AST:	Date:
ULN:	Date:
Serum Cr:	
Cr Cl:	

FEV1:	Date:
DLCO:	
Urine test:	Date:
Serum test:	

Contraception

19. Woman of childbearing potential (WOCBP): use two effective methods of contraception (hormonal or barrier method) or be surgically sterile, or abstain from heterosexual activity for the course of the study through 7 months post last dose of nivolumab.

- WOCBP defined as not being surgically sterilized or have not been free from menses for > 1 year.

Male: use two effective methods of contraception (barrier method) or abstain from heterosexual activity with the first dose of study therapy through 7 months post last dose of nivolumab.

Participant MRN (COH Only):

Participant Initials (F, M, L):

Institution:

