5.0 TREATMENT PROGRAM

5.1 Treatment Program Overview

This is a multi-center, open-label, Phase 2 clinical trial for participants with relapsed or refractory Hodgkin lymphoma who have undergone autologous stem cell transplant (ASCT). Participants will initiate protocol therapy within 30 to 60 days post stem cell reinfusion. Study PI can grant exception for a patient to start as late as 75 days post stem cell reinfusion with a reasonable justification for delay (e.g. recovery from post-ASCT toxicity) and this will not be a protocol deviation, nor require an exception to be filed. Nivolumab and brentuximab vedotin will be administered in an outpatient setting in each 21-day cycle.

Participants will receive up to 8 cycles of protocol therapy. If one agent is discontinued due to toxicity, then the participant may continue to receive single agent monotherapy.

Participants who complete protocol therapy ([Section 5.6](#)) will undergo follow-up ([Section 5.7](#)). Windows for all assessments and treatments are detailed in [Section 10.0](#).

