5.6 Duration of Therapy and Criteria for Removal from Study Treatment

Participants will receive protocol therapy until one of the below criteria are met:

- Disease progression
 - **Note:** Following consultation with the Study PI, participants who meet progression per 2014 Lugano classification [53] but who meet the criteria of "indeterminate response" (IR) according to the provisional modification to the 2014 Lugano Classification, the LYRIC

criteria [1] ([Appendix H](#)), and are deriving clinical benefit may continue to receive protocol therapy beyond progression as long as they meet the following criteria:

- Continue to meet treatment criteria
- Investigator-assessed clinical benefit and subject is tolerating study drug.
- Tolerance of study drug
- Stable performance status
- Treatment beyond progression will not delay an imminent intervention to prevent serious complications of disease progression (e.g., CNS metastases)
- *If the patient has IR per LYRIC criteria and is receiving therapy beyond progression:*
 - A confirmatory PET-CT should be performed within 12 weeks after initial progression to determine whether the patient meets PD criteria according to the LYRIC criteria [1].
 - Further progression is defined according to the LYRIC criteria
 - Protocol therapy should be discontinued permanently upon documentation of PD per the LYRIC criteria
- Participant receives 8 cycles (~ 6 months) of protocol therapy
- Unacceptable toxicity related to protocol therapy despite dose delay/ modification
 - **Note:** If one agent is delayed due to toxicity, then participants may continue with monotherapy for the other agent.
- General or specific changes in the participant's condition (including intercurrent illness) which render the participant unacceptable for further treatment in the judgment of the investigator
- Withdrawal of consent for further protocol therapy by the participant (See [Section 16.5](#))

Once participants meet criteria for removal from protocol therapy, the participant should then proceed to Follow-up.

Documentation of the reason for discontinuing protocol therapy and the date effective should be made in the medical record and appropriate eCRF. The COH DCC and the Study PI should be promptly notified of the change in participant status.

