6.2 Dose Modification/Delays

- Toxicities will be graded using the NCI [CTCAE v 4.0](#).
- Baseline values are from the last values obtained prior to treatment.
- If one agent is held due to toxicity for a given cycle, administration of the delayed agent should resume once the toxicity is resolved on the same schedule with the next cycle of combination therapy.
- If one agent is permanently discontinued, then the participant may continue monotherapy with the other agent.
- If both agents are held together and the toxicity lasts > 6 weeks, then protocol therapy will be discontinued.
- **Nivolumab dose management guidelines** are described in [Table 6.2.1](#).
 - Management algorithms for nivolumab have been developed to assist investigators in assessing and managing the following groups of AEs: Gastrointestinal, Renal, Pulmonary, Hepatic, Endocrinopathies, Skin, and Neurological. The algorithms have been incorporated into [Table 6.2.1](#) and can also be found in the Nivolumab IB. The guidance provided in these algorithms should not replace the Investigator's medical judgment but should complement it.
 - Dose reductions or dose escalations are not permitted for nivolumab.
 - Asterisk (*) in [Table 6.2.1](#): Following consultation with the Study PI, treatment delay > 6 weeks due to prolonged steroid taper is permissible.
 - Dosing interruptions or delays lasting > 6 weeks that occur for non-nivolumab-related reasons may be allowed if approved by the Study PI. Prior to re-initiating treatment in a participant with a dosing interruption lasting > 6 weeks, the Study PI must be consulted.

- **Brentuximab vedotin dose modification/ delay** are described in [Table 6.2.2](#).
 - Doses reduced for brentuximab vedotin-related toxicity should not be re-escalated without discussion with the Study PI.

Table 6.2.1 Dose management guidelines for Nivolumab

Toxicity	Nivolumab Dose Management Guidelines
Hematological Toxicity	
Anemia or thrombocytopenia Grade 3 Platelets: < 50,000 - 25,000/mm³	Continue nivolumab
Anemia or thrombocytopenia Grade 4 Platelets <25,000/mm³	
 • Hold nivolumab • Once toxicity resolves \leq Grade 2 resume nivolumab per protocol • Permanently discontinue if there is a treatment delay $>$ 6 weeks.
Neutropenia Grade 3 ANC <1000 - 500/mm³	
 • Continue nivolumab • Consider growth factor (G-CSF) support

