Grade 2-3 Creatinine > 1.5x baseline to $\leq 6 \times$ ULN	
 Hold the dose of nivolumab See Section 5.9.2.2 for supportive care. Resume therapy per protocol once the toxicity returns to Grade ≤ 1 and when steroid taper (≥ 1 month*) is complete. (* See exception in Section 6.2.) Discontinue treatment if toxicity lasts for > 6 weeks or unable to initiate steroid taper within a 6 week period. If elevations persist > 7 days or worsen: 
 Treat as Grade 4
Grade 4 Creatinine > 6x ULN	
 Discontinue nivolumab See Section 5.9.2.2 for supportive care.
Gastrointestinal (Diarrhea/ Colitis) Toxicity	
Diarrhea/Colitis Grade 1 Diarrhea: < 4 stools/day over baseline; Colitis: asymptomatic	
 Continue nivolumab. 
 See Section 5.9.2.3 for supportive care. If worsens: 
 Treat as Grade (G) 2 or 3/4
Diarrhea/Colitis Grade 2 Diarrhea: 4-6 stools per day over baseline; IV fluids indicated <24 hours (hrs); not interfering with ADL Colitis: abdominal pain; blood in stool	
 Hold the dose of nivolumab See Section 5.9.2.3 for supportive care. If toxicity resolves to Grade ≤ 1 within 5 days resume therapy with study regimen If persists $> 5-7$ days or recur: 
 Resume study regimen per protocol once the toxicity returns to Grade ≤ 1 and when steroid taper (≥ 1 month*) is complete. (* See exception in Section 6.2.) Discontinue treatment if toxicity lasts for > 6 weeks or unable to initiate steroid taper within a 6 week period. If worsens or persists $> 3-5$ days with oral steroids: 
 Treat as Grade 3-4

Toxicity	Nivolumab Dose Management Guidelines

Diarrhea/Colitis Grade 3-4
 
Diarrhea (G3): ≥7 stools per day over baseline; incontinence; IV fluids ≥24 hrs; interfering with activities of daily living (ADL)
 
Colitis (G3): severe abdominal pain, medical intervention indicated, peritoneal signs
 
G4: life-threatening, perforation
	
 • Discontinue study regimen • See Section 5.9.2.3 for supportive care.
Endocrinopathy	

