Grade 2	Continue nivolumab per protocol
Grade 3	
 Hold study agents Resume study regimen per protocol once toxicity returns to Grade ≤ 2 Discontinue treatment if toxicity lasts for > 6 weeks
Grade 4	Discontinue nivolumab
Amylase or Lipase elevation	
Grade 2	Continue nivolumab per protocol
Lipase or amylase Grade 3 Asymptomatic or not associated with clinical manifestations of pancreatitis	
 Continue nivolumab per protocol Consult the Study PI
Isolated Grade 4 amylase or lipase Asymptomatic or not associated with clinical manifestations of pancreatitis	
 Delay the dose of nivolumab until resolution to < Grade 2 Consult the Study PI If toxicity > 7 days from onset, discontinue therapy.
Lipase or amylase Grade 4 Symptomatic or associated with clinical manifestations of pancreatitis	
 Discontinue nivolumab
Laboratory abnormalities	
NOTE: Follow guidelines above for hematologic, hepatic (ALT, AST, total bilirubin), creatinine or amylase/lipase.	
Grade 2	Continue nivolumab per protocol
Grade 3	
 Delay the dose of nivolumab until resolution to \leq Grade 1 Discontinue treatment if toxicity lasts for > 6 weeks
Grade 4	Discontinue nivolumab if not an isolated Grade 4 event and is associated with clinical sequelae and are not corrected with supplementation/appropriate management within 72 hours of their onset.

Toxicity	Nivolumab Dose Management Guidelines
Immune-related (ir) AEs related to Nivolumab (Other than irAEs specified above)	
Note: See above sections for specific orientation regarding the following ir-related toxicities: eye related toxicities, ALT/AST/total bilirubin, creatinine, diarrhea/colitis, endocrinopathies, neurological, pulmonary, and skin.	
Grade 2	
 Hold nivolumab dose Resume study regimen per protocol once toxicity returns to Grade \leq 1 or baseline and if applicable, when steroid taper (\geq 1 month*) is complete. (* See exception in Section 6.2..) Discontinue treatment if toxicity lasts for $>$ 6 weeks or unable to initiate steroid taper within a 6 week period.
Grade 3 or 4	Discontinue nivolumab
Non-hematologic non-immune related toxicities related to Nivolumab (except fatigue and laboratory abnormalities)	

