7.7 Routine AE Reporting Guidelines

Routine AE reporting will occur via data entry into the study eCRF.

AEs reported through expedited processes (e.g., reported to the IRB, FDA, etc.) must also be reported in routine study data submissions.

AEs can be spontaneously reported or elicited during open-ended questioning, examination, or evaluation of a participant. (In order to prevent reporting bias, participants should not be questioned regarding the specific occurrence of one or more AEs.)

All AEs will be recorded from the initiation of protocol therapy through the follow-up period. The highest grade for any toxicity plus Grade 3 or 4 event for the same toxicity (if not the highest grade) will be reported during each cycle and during the safety follow-up period.

AE information recorded in the CRF include: Attribution to protocol therapy, grade and seriousness.

The collection of nonserious AE information should begin at initiation of protocol therapy up to a minimum of 100 days following the last dose of protocol therapy. Nonserious AEs should be followed to resolution or stabilization, or reported as SAEs if they become serious. Follow-up is also required for nonserious AEs that cause interruption or discontinuation of study drug and for those present at the end of study treatment as appropriate.

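### For men, criterion 19 sets no contraception period after the last brentuximab vedotin dose, so cover after that drug shrinks when nivolumab stops early (213 days down to 66 on schedule).

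*Combined protocol and SAP*

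**What the plan says.** Criterion 19 in Section 3.1 gives the contraception rule, and the synopsis repeats it. For men the period runs "with the first dose of study therapy through 7 months post last dose of nivolumab". For women it runs "for the course of the study through 7 months post last dose of nivolumab". Neither sentence mentions brentuximab vedotin, and no other section of the reviewed copy sets a contraception period for it. In Table 7.8.2, the pregnancy entry in the row after the 100-day visit also ends 7 months after the last nivolumab dose.

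Both drugs are study agents, and three sections allow one to be given without the other:

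- Section 5.1: "If one agent is discontinued due to toxicity, then the participant may continue to receive single agent monotherapy".
- Section 5.6: "If one agent is delayed due to toxicity, then participants may continue with monotherapy for the other agent".
- Section 6.2: "If one agent is permanently discontinued, then the participant may continue monotherapy with the other agent".

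The maximum is 8 cycles (Section 5.1) of 21 days, with a window of 3 days either way (Section 5.2). Table 6.2.1 makes stopping nivolumab alone a planned step. In the block headed "Immune-related (ir) AEs related to Nivolumab (Other than irAEs specified above", a Grade 3 or 4 event ends nivolumab only. The Grade 3-4 diarrhea/colitis row instead says "Discontinue study regimen".

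Section 16.6.1 states that brentuximab's effects on human embryogenesis, reproduction and spermatogenesis are not known.

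**The concern.** The period of protection after one drug is set by the stop date of a different drug. A man who loses nivolumab early to an immune-related event, and then takes brentuximab to Cycle 8, uses up most of his 7 months while still being dosed. The earlier nivolumab stops, the less cover remains after the last brentuximab dose, although his brentuximab exposure is the same as that of a man who received both drugs throughout.

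What is at stake is a safety margin for participants and their partners, for a drug whose effect on spermatogenesis the protocol calls unknown. The primary endpoint, the decision rule and the analysis are not involved.

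**Working it through.** The protocol gives no figure for cover after brentuximab, so there is none to reproduce. The check is date arithmetic.

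**Inputs**

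- Contraception period: 7 months after last nivolumab (criterion 19). 7 × 30.44 = 213 days.
- Cycle length: 21 days, 24 if the whole +3-day window is used (Section 5.2).
- Last possible brentuximab dose: Cycle 8 Day 1 (Section 5.1, Table 5.3).
- Half-life of the brentuximab conjugate: 4 to 6 days (Section 8.2.4). Nivolumab: about 26 days (Section 8.1.4).
- Post-dose exposure window for handling a discovered pregnancy: at least 6 half-lives (Section 7.4). It is used here for comparison only, because it is not a contraception rule.

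**Formula.** With last nivolumab at Cycle k and last brentuximab at Cycle 8, cover after brentuximab = 213 − L × (8 − k), where L is the cycle length.

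| Last nivolumab at cycle | Cover, L = 21 (days) | Cover, L = 24 (days) |
|---|---|---|
| 1 | 213 − 147 = 66 | 213 − 168 = 45 |
| 2 | 213 − 126 = 87 | 213 − 144 = 69 |
| 3 | 213 − 105 = 108 | 213 − 120 = 93 |
| 4 | 213 − 84 = 129 | 213 − 96 = 117 |
| 5 | 213 − 63 = 150 | 213 − 72 = 141 |
| 6 | 213 − 42 = 171 | 213 − 48 = 165 |
| 7 | 213 − 21 = 192 | 213 − 24 = 189 |
| 8 | 213 | 213 |

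**Against half-lives.** Six brentuximab half-lives are 6 × 4 = 24 to 6 × 6 = 36 days. The smallest on-schedule figures, 66 and 45 days, both exceed 36. At a 6-day half-life they equal 66 / 6 = 11 and 45 / 6 = 7.5 half-lives.

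**Effect of brentuximab delays.** Each day by which the last brentuximab dose slips removes a day of cover.

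- Cycle 1 case, 21-day cycles: cover falls below 36 days after more than 66 − 36 = 30 days of delay. It ends before the last brentuximab dose after more than 66 days.
- Cycle 1 case, every window used: the same limits are 45 − 36 = 9 days and 45 days.
- Cycle 2 case, 21-day cycles: cover falls below 36 days after more than 87 − 36 = 51 days of delay.
- Illustration, assuming one 6-week hold in the Cycle 1 case: 66 − 42 = 24 days, or 45 − 42 = 3 days with every window used.

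Such delays are possible under the plan. For Grade 3 neuropathy, Table 6.2.2 withholds brentuximab until the event improves and gives no maximum length in that row.

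**The case against.** The strongest reply is pharmacological. Nivolumab is the longer-lived drug: six of its half-lives are 6 × 26 = 156 days, against 24 to 36 for brentuximab. Timing the period from nivolumab is therefore a coherent choice. The on-schedule worst case leaves 11 brentuximab half-lives (at 6 days), while the full 7 months is about 213 / 26 = 8.2 nivolumab half-lives. This stands for participants treated on schedule. It does not settle the matter. Section 7.4 concerns a discovered pregnancy and not contraception, Section 8.2.4 gives no half-life for the released cytotoxic component, and the margin is not kept once brentuximab is delayed.

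The 66-day figure is also an extreme: one nivolumab dose, then every brentuximab dose to Cycle 8. With nivolumab stopped at Cycle 4, cover is 129 days. Continuing on one drug is optional, and the documents do not say how often it happens. All of this stands.

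A reader might infer more than the documents support:

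- *That men are left with unsafe cover.* No section states how long contraception must last after brentuximab, so no shortfall can be shown.
- *That 213 days is the proper period after brentuximab.* It is only what results when both drugs stop together.
- *That cover should be judged against the 100-day safety follow-up.* That is an adverse-event collection period and not a contraception standard.
- *That women have the same gap.* Their wording, "for the course of the study through 7 months post last dose of nivolumab", can be read as covering the whole study, and the synopsis puts participation at 18 months or more from the start of treatment. It still names no period tied to brentuximab.

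Brentuximab advice may also sit in the consent text or the package insert. The consent pages are not in the reviewed copy. Section 8.2 points to the insert for a description of the drug, which does not make it a contraception rule for this trial.

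**Conclusion.** The point holds for men as a minor gap in safety wording. Cover after the last brentuximab dose runs from 213 down to 66 days on schedule, or 45 days with every +3-day window used, depending only on when nivolumab stopped. On schedule this is a reduced margin, still above six brentuximab half-lives. In the Cycle 1 case it falls below 36 days with more than about 30 days of brentuximab delay. With more than about 66 days of delay, it ends before brentuximab does.

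These figures assume a month of 30.44 days, brentuximab continued to Cycle 8, and criterion 19 followed to the letter. The half-life comparison borrows the Section 7.4 window and the conjugate half-life. The wording and the arithmetic are certain. How many participants would be affected, and whether any would lack adequate protection, cannot be determined from the documents.

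**What to change.** In criterion 19 (Section 3.1 and the synopsis), choose one of two wordings:

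- run the period to 7 months after the last dose of protocol therapy, meaning nivolumab or brentuximab vedotin, whichever is given last; or
- run it to the later of 7 months after nivolumab and a period after brentuximab that the sponsor sets and justifies.

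For consistency, make the same change in the post-100-day row of Table 7.8.2, and check that the consent text matches. The protocol already counts from the last dose of either drug elsewhere: Section 7.7 collects non-serious adverse events "up to a minimum of 100 days following the last dose of protocol therapy".

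The first option gives about 213 days after the last dose of whichever drug finishes last. Its cost falls only on participants who finish on brentuximab alone: up to 147 more days of contraception on schedule (147 / 30.44 = 4.8 months), or 168 days with every window used (5.5 months). Brentuximab delays add to this day for day. The second option costs less if the brentuximab period is short: a period of 66 days or less adds nothing on the 21-day schedule. Either is a wording amendment in two places and one table row, with no effect on sample size, endpoint or analysis.
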